**Table 56: Laboratory Results by Parameter, Maximum Severity, Time Point, and Dose Cohort – Hemoglobin**

**Table 57: Laboratory Results by Parameter, Maximum Severity, Time Point, and Dose Cohort – WBC: Low**

**Table 58: Laboratory Results by Parameter, Maximum Severity, Time Point, and Dose Cohort – WBC: High**

**Table 59: Laboratory Results by Parameter, Maximum Severity, Time Point, and Dose Cohort – Platelets**

**Table 60: Laboratory Results Related to Study Treatment by Parameter, Maximum Severity, Time Point, and Dose Cohort – Any Hematology Parameter**

[Implementation note: we assume there are no missing grade, so removed the column "missing" from the table, if any missing found, we will add footnote to the table]

Time Point	Dose Cohort	N	None		Mild/ Grade 1		Moderate/ Grade 2		Severe/ Grade 3		Life-threatening/ Grade 4	
			n	%	n	%	n	%	n	%	n	%
Baseline	3 mg/kg EV68-228-N	x	x	xx	x	xx	x	xx	x	xx	x	xx
	10 mg/kg EV68-228-N											
	30 mg/kg EV68-228-N											
	Placebo											
Day 2	3 mg/kg EV68-228-N											
	10 mg/kg EV68-228-N											
	30 mg/kg EV68-228-N											
	Placebo											
Day 3	3 mg/kg EV68-228-N											
	10 mg/kg EV68-228-N											
	30 mg/kg EV68-228-N											
	Placebo											
Day 8	3 mg/kg EV68-228-N											
	10 mg/kg EV68-228-N											
	30 mg/kg EV68-228-N											
	Placebo											
Day 29	3 mg/kg EV68-228-N											
	10 mg/kg EV68-228-N											
	30 mg/kg EV68-228-N											
	Placebo											

**Table 60: Laboratory Results Related to Study Treatment by Parameter, Maximum Severity, Time Point, and Dose Cohort – Any Hematology Parameter (continued)**

Time Point	Dose Cohort	N	None		Mild/ Grade 1		Moderate/ Grade 2		Severe/ Grade 3		Life-threatening/ Grade 4	
			n	%	n	%	n	%	n	%	n	%
Max Severity Post Baseline	3 mg/kg EV68-228-N											
	10 mg/kg EV68-228-N											
	30 mg/kg EV68-228-N											
	Placebo											

Notes: The “Max Post Baseline” rows indicate the maximum severity experienced by each participant at any time point post baseline, including unscheduled assessments. N=Number of participants in the Safety Population.

Tables with similar format:

**Table 61: Laboratory Results Related to Study Treatment by Parameter, Maximum Severity, Time Point, and Dose Cohort – Hemoglobin**

**Table 62: Laboratory Results Related to Study Treatment by Parameter, Maximum Severity, Time Point, and Dose Cohort – WBC – Low**

**Table 63: Laboratory Results Related to Study Treatment by Parameter, Maximum Severity, Time Point, and Dose Cohort – WBC – High**

**Table 64: Laboratory Results Related to Study Treatment by Parameter, Maximum Severity, Time Point, and Dose Cohort – Platelets**

**Table 65: Laboratory Summary Statistics by Parameter, Time Point, and Dose Cohort – Hemoglobin**

Time Point	Dose Cohort	N	Mean	Standard Deviation	Median	Min, Max
Baseline	3 mg/kg EV68-228-N	x	xx.x	xx.x	xx.x	xx.x, xx.x
	10 mg/kg EV68-228-N					
	30 mg/kg EV68-228-N					
	Placebo					
Day 2	3 mg/kg EV68-228-N	x	xx.x	xx.x	xx.x	xx.x, xx.x
	10 mg/kg EV68-228-N					
	30 mg/kg EV68-228-N					
	Placebo					
Day 2, Change from Baseline	3 mg/kg EV68-228-N	x	xx.x	xx.x	xx.x	xx.x, xx.x
	10 mg/kg EV68-228-N					
	30 mg/kg EV68-228-N					
	Placebo					
Day 3	3 mg/kg EV68-228-N	x	xx.x	xx.x	xx.x	xx.x, xx.x
	10 mg/kg EV68-228-N					
	30 mg/kg EV68-228-N					
	Placebo					
Day 3, Change from Baseline	3 mg/kg EV68-228-N	x	xx.x	xx.x	xx.x	xx.x, xx.x
	10 mg/kg EV68-228-N					
	30 mg/kg EV68-228-N					
	Placebo					
Day 8	3 mg/kg EV68-228-N	x	xx.x	xx.x	xx.x	xx.x, xx.x
	10 mg/kg EV68-228-N					
	30 mg/kg EV68-228-N					
	Placebo					
Day 8, Change from Baseline	3 mg/kg EV68-228-N	x	xx.x	xx.x	xx.x	xx.x, xx.x
	10 mg/kg EV68-228-N					
	30 mg/kg EV68-228-N					
	Placebo					
Day 29	3 mg/kg EV68-228-N	x	xx.x	xx.x	xx.x	xx.x, xx.x
	10 mg/kg EV68-228-N					
	30 mg/kg EV68-228-N					
	Placebo					

**Table 65: Laboratory Summary Statistics by Parameter, Time Point, and Dose Cohort – Hemoglobin (continued)**

Time Point	Dose Cohort	N	Mean	Standard Deviation	Median	Min, Max
Day 29, Change from Baseline	3 mg/kg EV68-228-N	x	xx.x	xx.x	xx.x	xx.x, xx.x
	10 mg/kg EV68-228-N					
	30 mg/kg EV68-228-N					
	Placebo					

Note: N=Number of participants in the Safety Population with non-missing values at respective visit.

Tables with similar format:

**Table 66: Laboratory Summary Statistics by Parameter, Time Point, and Dose Cohort – WBC****Table 67: Laboratory Summary Statistics by Parameter, Time Point, and Dose Cohort – Platelets**

### 14.3.6 Displays of Vital Signs

**Table 68: Vital Signs by Maximum Severity, Time Point, and Dose Cohort – Any Assessment**

[Implementation note: we assume there are no missing grade, so removed the column "missing" from the table, if any missing found, we will add footnote to the table]

Time Point	Dose Cohort	N	None		Mild/ Grade 1		Moderate/ Grade 2		Severe/ Grade 3		Life-threatening/ Grade 4	
			n	%	n	%	n	%	n	%	n	%
Baseline	3 mg/kg EV68-228-N	x	x	xx	x	xx	x	xx	x	xx	x	xx
	10 mg/kg EV68-228-N											
	30 mg/kg EV68-228-N											
	Placebo											
15 Min After start of Infusion	3 mg/kg EV68-228-N											
	10 mg/kg EV68-228-N											
	30 mg/kg EV68-228-N											
	Placebo											
End of Infusion	3 mg/kg EV68-228-N											
	10 mg/kg EV68-228-N											
	30 mg/kg EV68-228-N											
	Placebo											
1 Hour After End of Infusion	3 mg/kg EV68-228-N											
	10 mg/kg EV68-228-N											
	30 mg/kg EV68-228-N											
	Placebo											
Day 2	3 mg/kg EV68-228-N											
	10 mg/kg EV68-228-N											
	30 mg/kg EV68-228-N											
	Placebo											
Day 3	3 mg/kg EV68-228-N											
	10 mg/kg EV68-228-N											
	30 mg/kg EV68-228-N											
	Placebo											

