### **4.4. Treatments**

#### **4.4.1. Treatments Administered**

Participants will receive a single IV dose of either study product or placebo. Infusions will be administered over approximately 15 minutes or 30 minutes, depending upon the volume of the infusion, in the absence of infusion reactions or non-drug, infusion related safety issues; longer infusion times will be permitted. All infusions must be completed within 4 hours of compounding.

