## 6. GENERAL STATISTICAL CONSIDERATIONS

### 6.1. General Principles

All continuous variables will be summarized using the following descriptive statistics: n (non-missing sample size), mean, SD, median, maximum and minimum. The frequency and percentages (based on the non-missing sample size) of observed levels will be reported for all categorical measures.

In general, all data will be listed, sorted by treatment, cohort, and participant, and when appropriate by visit number within participant. All summary tables will be structured with a column for each treatment in the order (3, 10, 30 mg/kg EV68-228-N, and Placebo) and will be annotated with the total population size relevant to that table/treatment, including any missing observations. In some safety tables, all participants who received active product (3, 10, 30 mg/kg EV68-228-N) will also be summarized together.

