a Conducted if visit occurs within 7 days of infusion.b VS will be collected to confirm eligibility prior to randomization and will be repeated, along with oximetry measurements, at approximately 15 minutes prior to infusion, the end of infusion, and at 1-hour post-infusion. For infusions lasting at least 30 minutes, these will also be collected at approximately 15 minutes after the beginning of the infusion.c During infusion and up to one-hour post-infusion, continuous cardio-pulmonary monitoring will be conducted to assess for acute changes. If a CS change occurs, the monitoring will be continued until it has resolved and it is deemed safe to discontinue monitoring by the site PI or designee.d Clinical screening laboratory evaluations will include WBCs, Hgb, PLT, Cr, ALT, and T. Bili. Clinical safety laboratory evaluations obtained on Days 1, 2, 3, 8, and 29 will include WBCs, Hgb, PLTs, Cr, ALT, and T. Bili. Results of laboratory studies collected prior to infusion on Day 1 do not require review prior to infusion; rather, they serve as a baseline assessment for post-infusion safety assessment.e Day 1 blood draws for ADA, hematology and chemistry should be done at the same time as the first PK blood draw, within 15 minutes prior to the infusion.f ECGs on Day 1 will occur approximately 15 minutes prior to infusion and 1-hour post-infusion.g For women of childbearing potential, a urine pregnancy test at screening and on Day 1 with results confirmed as negative prior to infusion.h If an infusion is terminated early, the remaining Day 1 PK samples will not be drawn and the PK and ADA samples at follow-up visits will not be drawn.i PK samples on Day 1 will be obtained approximately 15 minutes prior to infusion, at end of infusion (within a  $\pm$  5-minute window), and at 1-, 3-, and 5-hours post end of infusion, within a  $\pm$  15-minute window. Note, for infusions that last longer than 1-hour due to infusion related events or other disruptions in administration, see MOP for details on updating the PK collection timepoints.j PK sample will be collected within  $\pm$ 3-hour window of 24- and 48-hours after the end of infusion.k All participants will have a baseline sample taken for hypersensitivity testing approximately 15 minutes prior to infusion. For any participant that has an anaphylactic or anaphylactoid-type reaction, three additional samples will be taken: 1) at the onset of symptoms, 2) at 2 or more hours after onset, 3) at the resolution of symptoms.l Larger amount will be collected only if there is a hypersensitivity reaction.

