### 14.3.5 Displays of Laboratory Results

#### 14.3.5.1 Chemistry Results

**Table 44: Laboratory Results by Parameter, Maximum Severity, Time Point, and Dose Cohort – Any Chemistry Parameter**

[Implementation note: we assume there are no missing grade, so removed the column "missing" from the table, if any missing found, we will add footnote to the table]

Any Chemistry Parameter Time Point	Dose Cohort	N	None		Mild/ Grade 1		Moderate/ Grade 2		Severe/ Grade 3		Life-threatening/ Grade 4	
			n	%	n	%	n	%	n	%	n	%
Baseline	3 mg/kg EV68-228-N	x	x	xx	x	xx	x	xx	x	xx	x	xx
	10 mg/kg EV68-228-N											
	30 mg/kg EV68-228-N											
	Placebo											
Day 2	3 mg/kg EV68-228-N											
	10 mg/kg EV68-228-N											
	30 mg/kg EV68-228-N											
	Placebo											
Day 3	3 mg/kg EV68-228-N											
	10 mg/kg EV68-228-N											
	30 mg/kg EV68-228-N											
	Placebo											
Day 8	3 mg/kg EV68-228-N											
	10 mg/kg EV68-228-N											
	30 mg/kg EV68-228-N											
	Placebo											
Day 29	3 mg/kg EV68-228-N											
	10 mg/kg EV68-228-N											
	30 mg/kg EV68-228-N											
	Placebo											

**Table 44: Laboratory Results by Parameter, Maximum Severity, Time Point, and Dose Cohort – Any Chemistry Parameter (continued)**

Any Chemistry Parameter Time Point	Dose Cohort	N	None		Mild/ Grade 1		Moderate/ Grade 2		Severe/ Grade 3		Life-threatening/ Grade 4	
			n	%	n	%	n	%	n	%	n	%
Max Severity Post Baseline	3 mg/kg EV68-228-N											
	10 mg/kg EV68-228-N											
	30 mg/kg EV68-228-N											
	Placebo											

Notes: The “Max Severity Post Baseline” rows indicate the maximum severity experienced by each participant at any time point post baseline, including unscheduled assessments. N=Number of participants in the Safety Population.

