**Table 52: Laboratory Summary Statistics by Parameter, Time Point, and Dose Cohort – Creatinine**

Time Point	Dose Cohort	N	Mean	Standard Deviation	Median	Min, Max
Baseline	3 mg/kg EV68-228-N	x	xx.x	xx.x	xx.x	xx.x, xx.x
	10 mg/kg EV68-228-N					
	30 mg/kg EV68-228-N					
	Placebo					
Day 2	3 mg/kg EV68-228-N	x	xx.x	xx.x	xx.x	xx.x, xx.x
	10 mg/kg EV68-228-N					
	30 mg/kg EV68-228-N					
	Placebo					
Day 2, Change from Baseline	3 mg/kg EV68-228-N	x	xx.x	xx.x	xx.x	xx.x, xx.x
	10 mg/kg EV68-228-N					
	30 mg/kg EV68-228-N					
	Placebo					
Day 3	3 mg/kg EV68-228-N	x	xx.x	xx.x	xx.x	xx.x, xx.x
	10 mg/kg EV68-228-N					
	30 mg/kg EV68-228-N					
	Placebo					
Day 3, Change from Baseline	3 mg/kg EV68-228-N	x	xx.x	xx.x	xx.x	xx.x, xx.x
	10 mg/kg EV68-228-N					
	30 mg/kg EV68-228-N					
	Placebo					
Day 8	3 mg/kg EV68-228-N	x	xx.x	xx.x	xx.x	xx.x, xx.x
	10 mg/kg EV68-228-N					
	30 mg/kg EV68-228-N					
	Placebo					
Day 8, Change from Baseline	3 mg/kg EV68-228-N	x	xx.x	xx.x	xx.x	xx.x, xx.x
	10 mg/kg EV68-228-N					
	30 mg/kg EV68-228-N					
	Placebo					
Day 29	3 mg/kg EV68-228-N	x	xx.x	xx.x	xx.x	xx.x, xx.x
	10 mg/kg EV68-228-N					
	30 mg/kg EV68-228-N					
	Placebo					
Day 29, Change from Baseline	3 mg/kg EV68-228-N	x	xx.x	xx.x	xx.x	xx.x, xx.x
	10 mg/kg EV68-228-N					
	30 mg/kg EV68-228-N					
	Placebo					

Note: N=Number of participants in the Safety Population with non-missing values at respective visit.

Tables with similar format:

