**Table 68: Vital Signs by Maximum Severity, Time Point, and Dose Cohort – Any Assessment (continued)**

Time Point	Dose Cohort	N	None		Mild/ Grade 1		Moderate/ Grade 2		Severe/ Grade 3		Life-threatening/ Grade 4	
			n	%	n	%	n	%	n	%	n	%
Day 8	3 mg/kg EV68-228-N											
	10 mg/kg EV68-228-N											
	30 mg/kg EV68-228-N											
	Placebo											
Day 15	3 mg/kg EV68-228-N											
	10 mg/kg EV68-228-N											
	30 mg/kg EV68-228-N											
	Placebo											
Day 29	3 mg/kg EV68-228-N											
	10 mg/kg EV68-228-N											
	30 mg/kg EV68-228-N											
	Placebo											
Max Severity Post Baseline	3 mg/kg EV68-228-N											
	10 mg/kg EV68-228-N											
	30 mg/kg EV68-228-N											
	Placebo											

Notes: The “Max Severity Post Baseline” rows indicate the maximum severity experienced by each participant at any time point post baseline, including unscheduled assessments. N = Number of participants in the Safety Population.

Tables with similar format:

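### In the vital-sign grade tables (68-74), N is the whole Safety Population in a 15-minute row that is unmeasured by design for short infusions, so the percentage base is unclear

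*SAP*

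**What the plan says.** Table 68 summarises vital signs by maximum severity, time point and dose group. Tables 69-74 use the same format. The shell has an N column filled for each time point and group, then columns for no abnormality and Grades 1 to 4. Its implementation note reads "we assume there are no missing grade, so removed the column" for missing grades, and adds that a footnote will be supplied if any are found. The table note defines the column as "N = Number of participants in the Safety Population".

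One of the rows is the reading 15 minutes after the start of infusion, shown for all four groups. Footnote b of the Schedule of Activities (Table 2) limits that reading: "For infusions lasting at least 30 minutes, these will also be collected at approximately 15 minutes after the beginning of the infusion". Section 4.4.1 says: "Infusions will be administered over approximately 15 minutes or 30 minutes, depending upon the volume of the infusion".

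Two other places bear on the denominator:

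- Section 6.1 sets the general rule: "The frequency and percentages (based on the non-missing sample size) of observed levels will be reported for all categorical measures". It also says that summary tables are annotated with the total population size, missing observations included.
- The laboratory summary-statistics tables (52-54 and 65-67) use "N=Number of participants in the Safety Population with non-missing values at respective visit", and the ECG table (75) counts participants with measurements at the time points shown. The laboratory grade tables, such as Table 44, use "N=Number of participants in the Safety Population" with no such condition.

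**The concern.** The shell drops the missing column on an assumption that the SAP's own schedule contradicts. Anyone whose infusion lasts less than 30 minutes has no planned value in the 15-minute row, yet remains in N and falls in no grade column. This is known before any data arrive and does not depend on dropout or missed samples.

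At stake is how that row will be read. It is the only scheduled graded vital-sign reading during the infusion, in a first-in-human study whose primary objective is safety. Two programmers working from this SAP could print different percentages from the same data, and a reader of the finished table could not tell which base was used.

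**Working it through.** The SAP states no figure on this point, so there is none to reproduce. The check sets the passages side by side and then works through the arithmetic of the two possible denominators.

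**Step 1. Is the assumption of no missing grade consistent with the schedule?**

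- Table 68 has a 15-minute row for every group.
- Table 2, footnote b, collects that reading only for infusions of at least 30 minutes.
- Section 4.4.1 allows infusions of about 15 minutes, depending on volume.
- Section 4.5.1 does not list a 15-minute reading among the Day 1 vital signs.

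The assumption therefore fails for this row whenever a short infusion is given. The other rows of Table 68 are scheduled for everyone.

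**Step 2. What are the two denominators?**

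Let N be the number dosed in a group, m the number measured at 15 minutes and k the number with a graded abnormality.

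- Table-note base: k/N. The grade columns then add to m/N rather than 100%.
- Section 6.1 base: k/m.
- Ratio of the first to the second: m/N.

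Section 5 gives 10 participants per active dose and 6 on placebo, and Section 4.2 pools the placebo group across cohorts. The SAP does not say how many infusions will last at least 30 minutes, so m and k below are assumptions, shown over a range with k = 1.

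| Group | N | m (assumed) | k/N | k/m |
|---|---|---|---|---|
| Active | 10 | 2 | 10% | 50% |
| Active | 10 | 4 | 10% | 25% |
| Active | 10 | 5 | 10% | 20% |
| Active | 10 | 8 | 10% | 12.5% |
| Active | 10 | 10 | 10% | 10% |
| Placebo | 6 | 2 | 17% | 50% |
| Placebo | 6 | 4 | 17% | 25% |
| Placebo | 6 | 6 | 17% | 17% |

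With m = 4 of 10, the grade columns on the table-note base add to 4/10 = 40%. With m = 0, the row has no results, although N still prints as 10 or 6. With m = N the two bases agree.

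**Step 3. Do the laboratory grade tables share the problem?**

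Table 2 schedules chemistry and hematology for everyone on Days 1, 2, 3, 8 and 29, so nothing is missing by design in Tables 44-51 and 55-64. One missed placebo sample with one abnormality among the other five gives 1/6 = 17% on the table-note base and 1/5 = 20% on the Section 6.1 base. What remains is inconsistency: for the same parameter and visit, Tables 45 and 52 can print different values of N.

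**The case against.** The strongest reply is that Section 6.1 already settles the percentage base. It bases percentages on non-missing observations and treats the population total as an annotation. On that reading, a note giving N as the Safety Population is compatible with correct percentages, and the assumed example prints 25%, not 10%. No table note says that N is the denominator or that unmeasured participants count as having no abnormality. This stands: a reader might infer that the SAP prescribes diluted percentages, and it does not.

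The reply does not clear the shell. Section 6.1 describes tables with one column per treatment, whereas here the groups are rows and N is repeated at each time point, which makes it look like a denominator. If Section 6.1 governs, the table still does not show the number measured.

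The promised footnote is a real safeguard, but a partial one. It leaves N unchanged, is not said to give counts by row and group, and waits for the data to reveal a gap that the schedule already fixes.

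Three further points stand:

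- A reader might infer that a group with nobody measured would look like 0 of 10 abnormal. The column for no abnormality would also be zero, so an all-zero row with a footnote is confusing rather than falsely reassuring.
- End-of-infusion and 1-hour readings are taken for everyone, continuous cardiopulmonary monitoring runs until one hour after infusion, and Listing 15 shows every reading. The underlying data are not lost.
- The SAP gives no infusion volumes by cohort, so whether short infusions cluster in particular dose groups cannot be determined.

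**Conclusion.** The point holds in limited form and is minor. For the 15-minute row of Tables 68-74, the assumption behind removing the missing column is false by the SAP's own schedule, and the printed N either understates abnormal percentages or is not their denominator. The size depends on how many infusions last at least 30 minutes, which the document does not give. On the table-note base, the percentage is the correct one multiplied by m/N. On the Section 6.1 base, the percentage is unaffected and only the display is deficient.

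The document does not support extending the by-design problem to the laboratory tables. There the case rests on consistency and on incidental missing samples, and Section 6.5 expects missing data to be minimal.

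**What to change.** - In Tables 68-74, define N as participants in the Safety Population with a non-missing result at that time point. For the row of maximum severity after baseline, use participants with at least one post-baseline result. Tables 52 and 75 already define N by availability of the measurement.
- Label the 15-minute row: collected only for infusions lasting at least 30 minutes.
- Use the same N definition in Tables 44-51 and 55-64, so that they agree with Section 6.1 and with Tables 52-54 and 65-67.

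This changes footnotes, one row label and some programming. It alters no data collection. The one drawback is that N will differ between rows of the same table.

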**Table 68: Vital Signs by Maximum Severity, Time Point, and Dose Cohort – Any Assessment (continued)**

Time Point	Dose Cohort	N	None		Mild/ Grade 1		Moderate/ Grade 2		Severe/ Grade 3		Life-threatening/ Grade 4	
			n	%	n	%	n	%	n	%	n	%
Day 8	3 mg/kg EV68-228-N											
	10 mg/kg EV68-228-N											
	30 mg/kg EV68-228-N											
	Placebo											
Day 15	3 mg/kg EV68-228-N											
	10 mg/kg EV68-228-N											
	30 mg/kg EV68-228-N											
	Placebo											
Day 29	3 mg/kg EV68-228-N											
	10 mg/kg EV68-228-N											
	30 mg/kg EV68-228-N											
	Placebo											
Max Severity Post Baseline	3 mg/kg EV68-228-N											
	10 mg/kg EV68-228-N											
	30 mg/kg EV68-228-N											
	Placebo											

Notes: The “Max Severity Post Baseline” rows indicate the maximum severity experienced by each participant at any time point post baseline, including unscheduled assessments. N = Number of participants in the Safety Population.

Tables with similar format:

**Table 69: Vital Signs by Assessment, Maximum Severity, Time Point, and Dose Cohort – Body Temperature**

**Table 70: Vital Signs by Assessment, Maximum Severity, Time Point, and Dose Cohort – Pulse: High**

**Table 71: Vital Signs by Assessment, Maximum Severity, Time Point, and Dose Cohort – Pulse: Low**

**Table 72: Vital Signs by Assessment, Maximum Severity, Time Point, and Dose Cohort – Systolic Blood Pressure: High**

**Table 73: Vital Signs by Assessment, Maximum Severity, Time Point, and Dose Cohort – Systolic Blood Pressure: Low**

**Table 74: Vital Signs by Assessment, Maximum Severity, Time Point, and Dose Cohort – Diastolic Blood Pressure: High**

**Table 75: Summary of Post Dose ECG Change in Overall Interpretations from Baseline by Dose Cohort and Time Point**

Time Point	Change from Baseline in ECG Interpretation	3 mg/kg EV68-228-N	10 mg/kg EV68-228-N	30 mg/kg EV68-228-N	Placebo	All Participants
1 Hour post Infusion	N	x	x	x	x	x
	Normal at Both Times, n (%)	x (x)	x (x)	x (x)	x (x)	x (x)
	Normal to Abnormal, NCS, n (%)	x (x)	x (x)	x (x)	x (x)	x (x)
	Normal to Abnormal, CS, n (%)	x (x)	x (x)	x (x)	x (x)	x (x)
	Abnormal, NCS at Both Times, n (%)	x (x)	x (x)	x (x)	x (x)	x (x)
	Abnormal, NCS to Abnormal, CS, n (%)	x (x)	x (x)	x (x)	x (x)	x (x)
	Abnormal, NCS to Normal, n (%)	x(x)	x(x)	x(x)	x(x)	x(x)
Day 2	N	x	x	x	x	x
	Normal at Both Times, n (%)	x (x)	x (x)	x (x)	x (x)	x (x)
	Normal to Abnormal, NCS, n (%)	x (x)	x (x)	x (x)	x (x)	x (x)
	Normal to Abnormal, CS, n (%)	x (x)	x (x)	x (x)	x (x)	x (x)
	Abnormal, NCS at Both Times, n (%)	x (x)	x (x)	x (x)	x (x)	x (x)
	Abnormal, NCS to Abnormal, CS, n (%)	x (x)	x (x)	x (x)	x (x)	x (x)
	Abnormal, NCA to Normal, n (%)	x(x)	x(x)	x(x)	x(x)	x(x)

Notes: N=Number of participants in the Safety Population with ECG measurements at the time points indicated. NCS=Not clinically significant. CS=Clinically significant.

